4.2.7 Assignment of subjects to treatment groups

A total of 250 subjects were to be randomized to receive 135 µg VLA15 w/ alum, 180 µg VLA15 w/ alum or placebo according to the procedure described in section 4.2.9.

4.2.8 Subject Identification

At Visit 0 a 10-digit subject number was assigned to each subject. The first five digits are the study identifier (15202 for this study). The sixth and seventh digit is the site identification number (e.g. 01). The last three digits are assigned in ascending order as the subjects are screened.

4.2.9 Randomization

Subjects were to be allocated to treatment groups via the EDC system. Eligible subjects were to be randomized 2:2:1 stratified by study site, age group and baseline *B.b.* s.I. serostatus according to a randomization list created by a statistician. Date and time of enrollment were to be defined as the time point at which the subject is registered in the system and the subject is allocated to a treatment group.

^{*} From the 18th birthday until the last day before the 66th birthday

[†] From the 18th birthday until the last day before the 50th birthday

[‡] From the 50th birthday until the last day before the 66th birthday

All eligible subjects enrolled in the Booster Phase will be randomized 2:1 to receive an additional VLA15 180 µg vaccination or Placebo according to a randomization list created by a statistician.

4.2.10 Blinding

The study is an observer-blinded trial, which is conducted in a blinded manner for the study investigators, the sponsor including laboratory personnel, and the subjects. Only designated study staff who randomize subjects into treatment groups and perform preparation and application of the vaccinations are unblinded. These unblinded study staff members are not involved with trial conduct otherwise. An overview of persons who is unblinded is provided below:

Unblinded:

- Designated study site staff who randomize subjects to treatment groups and are concerned with IMP handling (i.e. perform preparation and administration of the study vaccine, maintain drug dispensing log detailing the dates and quantities of IMP administered to each subject). These unblinded study staff members are not involved with trial conduct otherwise.
- CRAs responsible for monitoring of IMP handling and related data for verifying drug accountability during the study and performing overall drug accountability.
- Statistical team at the CRO performing statistical analyses for generation of safety data tables for the DSMB.
- DSMB members.

Blinded:

- Study participants
- Investigators and other study staff involved in general study conduct and safety assessments.
- All other CRAs (responsible for monitoring study data apart from IMP handling/drug accountability).
- All other sponsor/collaboration partner and CRO staff including laboratory personnel at the sponsor's labs for immunogenicity assessments.

Blinding process:

To ensure that study participants cannot tell the group they have been allocated to from the physical appearance and the content of the syringe, preparation of IMP must be done by unblinded staff members only in a separate room, unobserved by blinded staff members and the subject. After drawing the respective injection volume into syringes and visual check, the syringe content is masked by covering the syringe with a white, non-see-through adhesive label wrapped around the syringe.

Unblinding during the study:

The blind must not be broken for anyone involved in the trial conduct. Unblinding of individual cases can be performed by the investigator in case of emergency and if knowledge of the treatment assignment is mandatory for emergency treatment. Designated personnel at the CCI /Pfizer safety and a sponsor representative otherwise not involved in the study conduct may be unblinded for individual cases of SAEs that are both unexpected and suspected to have a causal relationship to the trial vaccines (SUSARs), to fulfil safety reporting requirements. Procedures are described in a safety management plan. The same blinding/emergency unblinding procedures as in the Main Study Phase will be applied during the Booster Phase.

The study sponsor/collaboration partner and trial statisticians will be unblinded at the time of the Day 208 Interim Analysis (primary endpoint analysis), after the respective database

snapshot has been performed. All other study personnel including investigators and other study staff involved in general study conduct and safety assessments as well as laboratory personnel who are performing analytical assays remain blinded and will remain blinded until start of Month 18 visits (Visit 8). As only subjects randomized in the 180 µg dose group during the Main Study Phase will be included in the Booster Phase, partial unblinding of the study site staff and subjects will occur, as subjects that will be asked to continue the study will know that they had been randomized to the VLA15 180 µg group in the Main Study Phase. Investigators will be informed shortly prior to the start of Visit 8 which subjects they should ask to continue in the study via a list of subjects that will be provided by Data Management. Investigators and other site staff will therefore be partially unblinded shortly prior to Visit 8. Subjects who are not being invited will not be able to ascertain if they have been enrolled to the VLA15 135 µg group or the placebo group. Booster subjects, sponsor and investigator/site staff involved in clinical evaluation of subjects will however be blinded for the Booster Phase, i.e., they will not know if subjects that continue the study in the Booster Phase will receive VLA15 180 µg or Placebo.

In the Booster Phase the study sponsor/collaboration partner and trial statisticians will be unblinded at the time of the Month 19 analysis, after the respective database snapshot has been performed.

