7. ASSESSMENT OF IMMUNOGENICITY

7.1 Immunogenicity Measurements

Immunogenicity assessments measuring OspA serotype specific by IgG ELISA are performed on samples collected at Visits 1-12, or at respective unscheduled visits after Visit 7 or 8, if one or more of these visits are performed remotely (e.g., phone/ video calls).

[figure not shown]
All steps of the assays are performed at Valneva Austria GmbH Vienna, Department of Clinical Serology according to Standard Operating Procedures (SOPs). The work is performed in an environment that is certified to Biological Safety Level 2 (BSL2), internally audited, and conform to GCLP requirements. Raw data is stored on a separate, secure server in a defined Information Technology environment complying with regulatory standards. Raw data print outs are stored in respective study binders.

Details on the analysis of immunogenicity assessments described below will be provided in the Statistical Analysis Plan (SAP).

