9.3 Immunogenicity Analysis

Immunogenicity analyses include the analysis of OspA serotype (ST1 to ST6) specific IgG levels by ELISA and by a serum bactericidal assay (SBA).

Main Study Phase:

The primary immunogenicity analysis will compare the Geometric Mean Titers (GMTs) of serotype specific IgG against each OspA ST1 to ST6 as determined by ELISA in the PP population between the treatment groups VLA15 w/ alum 135 µg and VLA15 w/ alum 180 µg and between the VLA15 treatment groups and the placebo group, respectively, on Day 208. GMTs and GMT ratios will be estimated by applying an analysis of variance (ANOVA) including the factor treatment group and study site. This will be done using log10 transformed data and taking the anti-log of the resulting point estimates for the least squares means, least squares means differences and the corresponding 95% CIs. Tukey's HSD test will be applied for pair-wise comparisons. In addition, sensitivity analyses (ANOVAs with factors study site, treatment group, study site*treatment group, age, and *B.b. s.I* serostatus at baseline) will be performed.

As secondary analysis, GMTs and GMT ratios will be analyzed by ELISA as outlined above on Day 1, 29, 57, 85, 180, 208, 365 and 545. Analyses will compare both dose groups against each other and against the placebo group.

Further secondary immunogenicity analyses will compare the following:

- The Geometric Mean of the fold rise as compared to baseline (GMFR) for IgG against each OspA ST 1-6 as determined by ELISA (ANOVA).
- Seroconversion Rates against each OspA serotype separately; against all six OspA serotypes combined and against OspA ST1 and ST2 combined. Seroconversion rates will be compared using Fisher-Freeman-Halton tests, a significant overall test will be amended by pair-wise tests (Fisher's exact test).
 - For ELISA: SCR is defined as rate of subjects that change from seronegative* at Visit 1 (baseline) to seropositive†, if seronegative at baseline, or that achieve a four-fold increase in IgG titer compared to baseline, if seropositive at Visit 1
 - For functional antibody testing (SBA): SCR is defined as rate of subjects that change from seronegative to seropositive CCI or as a > 4-fold rise in IgG antibody titer from Visit 1 for subjects that are seropositive at Visit 1 (baseline).
- GMTs, SCRs and GMFRs for IgG against each OspA serotype (ST1 to ST6), determined by ELISA, at Day 1, 29, 57, 85, 180, 208, 365 and 545, stratified by age group.

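### Section 4.2.10 keeps the assay laboratory blinded only until Visit 8 starts, although the Month 18 samples compared across the three arms are drawn at or after that visit

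*Protocol*

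**What the plan says.** Section 4.2.10 of the protocol opens with an overview of who is and is not blinded. The blinded list includes "All other sponsor/collaboration partner and CRO staff including laboratory personnel at the sponsor's labs for immunogenicity assessments". Timing comes later in the section. At the Day 208 interim analysis the sponsor, its collaboration partner and the trial statisticians are unblinded. Other study personnel are not, and among them "laboratory personnel who are performing analytical assays remain blinded and will remain blinded until start of Month 18 visits (Visit 8").

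The section then explains what happens at Visit 8. Only 180 µg subjects go on to the booster, so "partial unblinding of the study site staff and subjects will occur", and Data Management sends investigators a list of whom to invite. For the Booster Phase, "The same blinding/emergency unblinding procedures as in the Main Study Phase will be applied during the Booster Phase". Later, "In the Booster Phase the study sponsor/collaboration partner and trial statisticians will be unblinded at the time of the Month 19 analysis".

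On the laboratory itself, section 7.1 states: "All steps of the assays are performed at Valneva Austria GmbH Vienna, Department of Clinical Serology". On the analysis, section 9.3 plans that "GMTs and GMT ratios will be analyzed by ELISA as outlined above on Day 1, 29, 57, 85, 180, 208, 365 and 545", comparing both doses with each other and with placebo.

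**The concern.** Blinding the people who run the assay prevents knowledge of the arm from influencing repeat testing, the handling of out-of-range results or the acceptance of plates. That protection is needed until the last sample in a comparison has been measured. Here the stated end point falls before the Month 18 samples can be assayed, and the reason given for unblinding does not apply to the laboratory, which invites no one.

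At stake are the Day 545 secondary endpoints (GMT, GMFR and seroconversion for six serotypes across three arms). The same Visit 8 sample also normally serves as the pre-booster value: footnote 9 of Table 4 asks for a new sample only if Visit 9 is more than one month after Visit 8.

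**Working it through.** The protocol gives no figure for this point. The check is one of timing, followed by an illustration of size.

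**Timing of the Month 18 assays**

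- Laboratory blind as written: ends when the Month 18 visits start (section 4.2.10).
- Month 18 sample: taken at Visit 8, Day 545 ± 28 days. If Visit 8 is remote, it is taken at an unscheduled visit within one month afterwards (section 4.2.3).
- The earliest possible Visit 8 is Day 545 − 28 = Day 517. No Month 18 sample exists before Visit 8, so none can be assayed before the stated end of the blind.

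**What can still be changed**

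- This protocol version is dated 02-Nov-2021.
- Main Study Phase: July 2019 start + 22 months gives about May 2021. Month 18 visits should be over.
- Month 30: boosters start in January 2021 and Visit 12 is Visit 9 + 12 months ± 28 days (Table 4). Taking 1 January 2021 as the earliest Visit 9, 1 January 2022 − 28 days = 4 December 2021, which is 32 days after the protocol date. No Month 30 sample can be earlier.
- Visit 9 by about July 2021 (May + at most 2 months) and Visit 10 at + 28 days put the Month 19 unblinding at about August 2021, before any Month 30 sample.

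**Illustration of size, Month 18, 135 µg against 180 µg**

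Inputs: SD 0.51 log10 and 90 evaluable per dose arm (section 9.6); five sites (section 4.2.4); 45 evaluable placebo subjects (assumed, 50 less 10%). The test is the one in section 9.3: "Tukey's HSD test will be applied for pair-wise comparisons".

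- SE of the log10 GMT difference = 0.51 × √(2/90) = 0.0760.
- Error df = 225 − 3 − 4 = 218. The Tukey quantile for three groups is 3.337, so the critical value is 3.337/√2 = 2.360.
- An assumed systematic titer shift in one arm, divided by the SE, gives the noncentrality of the t statistic:

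| Assumed shift | log10(shift)/SE | False-positive rate for this pair |
|---|---|---|
| none | 0 | 1.9% |
| 5% | 0.28 | 2.4% |
| 10% | 0.54 | 3.8% |
| 20% | 1.04 | 9.6% |

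A shift of about 13% would bring the pair to 5%.

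**Illustration of size, Month 30, booster against placebo**

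The stated maximum of 81 subjects, randomized 2:1, gives 54 and 27.

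- SE = 0.51 × √(1/54 + 1/27) = 0.1202.
- Shifts of 5%, 10% and 20% equal 0.18, 0.34 and 0.66 SE.
- The 95% CI half-width is 1.992 × 0.1202 = 0.2395 log10, a factor of 10^0.2395 = 1.74 either way.

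The assumed shifts are small against that interval, so a large booster contrast would not be altered.

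**The case against.** The strongest reply is that the Visit 8 clause is loose drafting. It covers site staff and laboratory staff in one breath, and the following sentences describe disclosure to site staff and subjects only. No route is described by which a code reaches the laboratory, and the unblinding text opens with a general rule against breaking the blind. This is plausible, and it means that no planned unblinding of the laboratory has been shown. It does not remove the stated end date, which names assay personnel expressly.

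The assay also has its own safeguards. It is validated and read against a reference curve (section 7.1.1), and it runs under SOPs in an audited laboratory that conforms to GCLP (section 7.1). These limit how far knowledge of the arm could move a titer. The shifts above have no source in the protocol, and the SD comes from Phase 1 under a different schedule.

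Three stronger readings may tempt a reader, and the document does not support them.

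- **Section 4.2.10 contradicts itself because the blinded list has no end date.** No entry in that list has one. It is an overview, and timing follows later in the section.
- **The laboratory loses its blind at Month 19.** The assays are run in-house, and the section's opening counts laboratory personnel with the sponsor. But at Day 208 the section unblinds the sponsor and collaboration partner while keeping assay personnel blinded as other study personnel. The Month 19 sentence uses the same term, and the main-phase procedures carry over. Only a clarification is wanted.
- **AESI adjudication is compromised because DSMB members are unblinded.** The order in which they see the case and the code is a matter for the DSMB charter, which section 8.6.1 says describes processes in detail and which is not at hand. No conclusion can be drawn.

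**Conclusion.** The point stands in a narrow form. As written, the assay laboratory's blind ends before any Month 18 sample can be measured, and the reason given for unblinding at Visit 8 does not cover the laboratory. This is a minor improvement to the wording; it is not evidence of biased results.

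Only secondary endpoints are touched. The protocol already reports Day 208 titers, measured while the laboratory was to be blinded, and the dose was chosen on those data (sections 4.2.2 and 9.5). Ending the main-phase blind at Visit 8 does not reveal the booster allocation, which is made at Visit 9. Whether samples from other visits, such as Day 365, were still unassayed when Visit 8 began is not stated, so wider exposure is not established.

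The false-positive figures rest on assumed shifts, the Phase 1 SD and an assumed placebo count. They show scale only. The case for change is that the safeguard is nearly free and the wording could still cover every Month 30 assay, up to 81 × 6 = 486 titers.

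**What to change.** In section 4.2.10:

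1. Limit the Visit 8 end point to site staff and subjects.
2. State that assay laboratory personnel remain blinded to main-phase and booster allocation until all assay results through Month 30 are final.
3. For clarity, repeat the Day 208 laboratory exception in the Month 19 unblinding sentence.

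In the study report, state whether the Month 18 assays, and any Month 24 assays already run, were performed blind. For Month 18 this disclosure is probably all that remains possible.

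The cost is an amendment to one section, submitted to the competent authority and IRB/IEC as section 14.1 requires, and one sentence in the report. No new staff or data are needed. If the laboratory was always meant to stay blinded, the change only writes down existing practice.

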- + GMTs, SCRs for IgG against each OspA serotype (ST1 to ST6), determined by ELISA, at Day 1 (Month 0), 29 (Month 1), 57 (Month 2), 85 (Month 3), 180 (Month 6), 208

[†] An ELISA titer below 40 U/mL (i.e., the quantitation limit of the ELISA) is considered "OspA IgG seronegative". Values will be replaced by 20 U/mL.

[†] An ELISA ≥40 U/mL is considered "OspA IgG seropositive".

(Month 7), 365 (Month 12), and 545 (Month 18), Month 19, Month 24 and Month 30, stratified by age group.

Safety:**Main Study Phase:**

- + Frequency of SAEs during the entire Main Study Phase;
- + Frequency of related SAEs during the entire Main Study Phase;
- + Frequency of AESIs during the entire Main Study Phase;
- + Frequency of related AESIs during the entire Main Study Phase;
- + Frequency of unsolicited AEs during the entire Main Study Phase (incl. clinically relevant laboratory parameters);
- + Frequency of related unsolicited AEs during the entire Main Study Phase (incl. clinically relevant laboratory parameters);
- + Frequency of solicited local and solicited systemic AEs within 7 days after each and after any vaccination.
- + Frequency of SAEs, AESIs, solicited and unsolicited AEs during the entire Main Study Phase stratified by age group.

Booster Phase (applicable for a subset of subjects participating in booster phase):

- + Frequency of SAEs during the entire Booster Phase;
- + Frequency of related SAEs during the entire Booster Phase;
- + Frequency of AESIs during the entire Booster Phase;
- + Frequency of related AESIs during the entire Booster Phase;
- + Frequency of unsolicited AEs (incl. clinically relevant laboratory parameters) up to Month 19;
- + Frequency of related unsolicited AEs (incl. clinically relevant laboratory parameters) up to Month 19;
- + Frequency of solicited local and solicited systemic AEs within 7 days after booster vaccination.
- + Frequency of SAEs, AESIs, solicited and unsolicited AEs, stratified by age group.

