- Review of Subject Diary: Ask subject to read through diary, or to mail or email pictures of the diary entries upfront to aid the discussion. Instruct subject to continue using the diary for documenting AEs and to bring the diary along for the next in-person subject visit.
- Instruct subject to immediately inform the site in case subject experiences one of the following:
 - any severe adverse event
 - any symptoms suspicion or diagnosis of Lyme borreliosis, e.g. red or bluish-red patch (≥ 5 cm, indicate location), or joint swelling (indicate which joint).
- Perform scripted safety assessment. Record any unsolicited AEs since the last study visit.

Visit 7, Day 365/ Month 12 (+7/- 14 days):

This visit should preferably be conducted as an in-person visit. If an in-person is not feasible due to COVID-19, e.g. travel restrictions, local recommendations, circumstances at the study site's location that prohibit an in-person visit, or if the PI believes that the subject's safety and well-being might be jeopardized with an in-person visit at the study site due to COVID-19, the visit should be conducted remotely (e.g., phone/ video call).

For in-person visits:

- Document any changes to concomitant medication/treatments including vaccination(s) since the previous study visit.
- Perform symptom-driven physical examination.
- Review and collect Diary (if not returned yet due to previous visits performed remotely)/ Memory Aid, including verification of entries with the subject.
- Record any unsolicited AEs since the last study visit.
- Distribute and explain Memory Aid to document unsolicited Adverse Events. Instruct subject to immediately inform the site in case the subject experiences any severe symptoms or if subject has any suspicion of having Lyme borreliosis.
- Laboratory tests:
 - Urine pregnancy test: In women of childbearing potential.
- Collect immunogenicity blood sample.

For remote visits:

- Document any changes to concomitant medication/treatments including vaccination(s) since the previous study visit.
- Review of Memory Aid: Ask subject to read through memory aid/ AE sections of subject diary if previous visit was conducted as remotely, or to mail or email pictures of the memory/diary entries upfront to aid the discussion. Instruct subject to continue using the memory aid/diary for documenting AEs and to bring the memory aid/diary along for the next study visit.

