- Instruct subject to immediately inform the site in case subject experiences one of the following:
 - any severe adverse event
 - any symptoms suspicion or diagnosis of Lyme borreliosis, e.g. red or bluish-red patch (≥ 5 cm, indicate location), or joint swelling (indicate which joint).
- Perform scripted safety assessment. Record any unsolicited AEs since the last study visit.

In case the subject visit is performed remotely and the COVID-19 situation allows coming to the site at a later time point, the immunogenicity sample should be taken during an unscheduled visit as early as possible within a maximum time window of 2 months after the V7 remote study visit.

Visit 8, Day 545/ Month 18 (+/- 28 days):

This visit should preferably be conducted as an in-person visit. If an in-person is not feasible due to COVID-19, e.g. travel restrictions, local recommendations, circumstances at the study site's location that prohibit an in-person visit, or if the PI believes that the subject's safety and well-being might be jeopardized with an in-person visit at the study site due to COVID-19, the visit should be conducted remotely (e.g., phone/ video call).

For in-person visits:

- Document any changes to concomitant medication/treatments including vaccination(s) since the previous study visit.
- Perform symptom-driven physical examination.
- Review and collect Memory Aid, including verification of entries with the subject.
- Record any unsolicited AEs since the last study visit.
- Laboratory tests:
 - Lyme borreliosis screening test: For serological screening on infection with Lyme borreliosis, a commercially available Lyme borreliosis screening test will be performed. Serum samples that are tested positive will be verified by a confirmatory immunoblot.
 - Urine pregnancy test: In women of childbearing potential.
 - Clinical Chemistry: Creatinine, sodium, potassium, calcium, aspartate aminotransferase (AST), alanine aminotransferase (ALT), alkaline phosphatase, bilirubin, CRP.
 - Hematology: Hemoglobin, hematocrit, erythrocyte count, white blood count, platelets.
 - Urinalysis (standard urine dipstick): pH, specific gravity, leucocytes, nitrite, protein, glucose, ketones, urobilinogen, bilirubin, erythrocytes.
- Collect immunogenicity blood sample.

For remote visits

- Document any changes to concomitant medication/treatments including vaccination(s) since the previous study visit.

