- Review of Memory Aid: Ask subject to read through memory aid/ AE sections of subject diary if previous visits were conducted as remote study visits, or to mail or email pictures of the memory/diary entries upfront to aid the discussion.
- Perform scripted safety assessment. Record any unsolicited AEs since the last study visit.
- Inform subjects of the possibility of an unscheduled visit within 1 month after the remote visit for immunogenicity sample collection, if the COVID19 situation allows.
- If the COVID-19 situation allows coming to the site for an unscheduled visit within 1 month after the remote visit: take immunogenicity sample.

The following procedures are performed for subjects enrolled in the Booster Phase:

Visit 9, Month 18 (Date of Visit 8 (+ 2 max. months)):

Visit 8 and Visit 9 should be combined in one visit if possible; otherwise the time between Visit 8 and Visit 9 should be kept as short as possible (preferably maximum of one month apart). If the COVID19 pandemic mandates, the subject has the possibility to perform the study visit within 2 months after Visit 8. If both visits are scheduled on the same day, all procedures from Visit 8 have to be performed prior to performing procedures from Visit 9.

Signed and dated informed consent for the Booster Phase must be obtained before any study specific procedures are undertaken.

- Check of inclusion and exclusion criteria.
- Check vaccination delay criteria.
- Document any changes to concomitant medication/treatments including vaccination(s) since the Visit 8.
- Perform symptom-driven physical examination, measure vital signs (systolic and diastolic blood pressure, pulse rate) in seated position and at rest, measure oral body temperature (vaccination should be postponed in case of an acute febrile illness).
- Laboratory tests (samples to be taken prior to vaccination):
 - Lyme borreliosis screening test (only to be performed if Visit 9 is later than 1 month after Visit 8): For serological screening on previous infection with Lyme borreliosis, a commercially available Lyme borreliosis screening test will be performed. Serum samples that are tested positive will be verified by a confirmatory immunoblot.
 - Urine pregnancy test: In women of childbearing potential.
 - Urinalysis (standard urine dipstick): pH, specific gravity, leucocytes, nitrite, protein, glucose, ketones, urobilinogen, bilirubin, erythrocytes.

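### Unsolicited AEs and laboratory findings first assessed at Visit 8 are judged after site staff learn which booster-eligible subjects received 180 µg

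*Protocol*

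**What the plan says.** Protocol section 4.2.10 lists investigators and the staff who carry out safety assessments as blinded, and keeps them blinded until the Month 18 visits begin. It then describes how that ends: "Investigators will be informed shortly prior to the start of Visit 8 which subjects they should ask to continue in the study via a list" supplied by Data Management. Only 180 µg subjects can be on the list, so the section concludes: "Investigators and other site staff will therefore be partially unblinded shortly prior to Visit 8". It adds that invited subjects will know they had been in the 180 µg group. For the others it says: "Subjects who are not being invited will not be able to ascertain if they have been enrolled to the VLA15 135 µg group" or to placebo.

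Visit 8 is the last Main Study visit. Section 4.2.3 has the site review the Memory Aid, take safety laboratory samples and carry out this step: "Record any unsolicited AEs since the last study visit". The previous scheduled contact is "Visit 7, Day 365/ Month 12 (+7/- 14 days"). Section 8.4.1 makes the investigator responsible for causality and severity, and section 8.5 also leaves the clinical relevance of abnormal laboratory values to the investigator.

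These judgements feed a secondary endpoint in section 4.1: "Frequency of related unsolicited AEs during the entire Main Study Phase (incl. clinically relevant laboratory parameters"). Section 9.4 tests AE rates, including related unsolicited AEs, between groups up to Day 545 with Fisher's exact (Fisher-Freeman-Halton) test.

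**The concern.** Whether an event is recorded, called related, or called clinically relevant is a matter of judgement, and observer blinding exists to protect such judgements. At Visit 8 the assessor may know that the subject in front of them received 180 µg, and the subject may know it too. The arm identified is the one selected for further development. Any shift in eliciting or attributing events at that visit would therefore fall on the comparison of most interest.

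The early disclosure also appears unnecessary for the assessments themselves. Booster consent, eligibility checks and randomization all belong to Visit 9, and for combined days section 4.2.3 already fixes the order: "If both visits are scheduled on the same day, all procedures from Visit 8 have to be performed prior to performing procedures from Visit 9". Nothing ties release of the list to completion of the Visit 8 safety entries. Section 4.2.10 does not say whether a site receives one list for all its subjects or is told subject by subject. A single list would lengthen the exposed period for subjects whose Visit 8 comes later.

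**Working it through.** The protocol gives no figure for the extent of this unblinding, so there is none to reproduce. The check uses the visit schedule and the subject counts.

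**Look-back at Visit 8** (section 4.2.3: Visit 7 at Day 365, +7/−14 days; Visit 8 at Day 545, ±28 days)

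- Nominal: 545 − 365 = 180 days.
- Shortest: (545 − 28) − (365 + 7) = 517 − 372 = 145 days.
- Longest: (545 + 28) − (365 − 14) = 573 − 351 = 222 days.
- Share of Day 1 to Day 545: 180 / 544 = 33%.

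**Who is identified** (section 1.4.3.2: 97 on 135 µg, 98 on 180 µg, 51 on placebo, total 246; section 4.2.4: at most 81 booster participants)

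Booster inclusion criterion 2 limits the list to 180 µg subjects in the Day 208 per-protocol population. I assume a list of 81. The protocol gives this as an estimate of participants, not as the length of the list.

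- Identified: 81 / 98 = 83% of the 180 µg arm.
- Not on the list: 246 − 81 = 165, made up of 97 on 135 µg, 51 on placebo and 98 − 81 = 17 on 180 µg.
- Chance that an unlisted subject is on 180 µg: 17 / 165 = 10%, against 98 / 246 = 40% before the list.
- Chance that an unlisted subject is on placebo: 51 / 165 = 31%, against 51 / 246 = 21% before.

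These shares use randomized counts and ignore dropout before Visit 8. Absence from the list is therefore informative, but it does not separate 135 µg, placebo and the excluded 180 µg subjects.

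**Which events are exposed**

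- Severe symptoms and suspected Lyme borreliosis: at Visit 7 subjects are told to inform the site immediately (section 4.2.3). SAEs are to be reported within 24 hours of awareness (section 8.4.4). When these are handled before the list arrives, they are assessed blind.
- Other unsolicited AEs: written in the Memory Aid and first reviewed by the site at Visit 8. Exposed.
- Visit 8 laboratory results: judged for clinical relevance at or after Visit 8. Exposed.
- Solicited AEs: collected in the seven days from each vaccination, the last at Day 180. Not exposed.
- Primary endpoint: Day 208 ELISA titers. Not exposed.

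**The case against.** The strongest reply has four parts.

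1. **The unblinding is disclosed.** Section 4.2.10 states it, its reason and its limits as the price of a booster phase drawn from one arm. That is correct: this is a design choice, not an internal contradiction. The section offers no safeguard or analysis to go with it.

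2. **The scope for bias is limited.** The affected events arise roughly 6 to 12 months after the Day 180 dose, and section 8.4.2.6 asks for a plausible temporal sequence before calling an event possible or probable. The Lyme and AESI questions are scripted, and the DSMB makes the final adjudication of AESIs. All of this narrows the effect. It does not cover routine unsolicited AEs or laboratory relevance, which stay with the investigator.

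3. **The remedy may come late, and much of it exists.** This version is dated 02-Nov-2021. A July 2019 start plus the estimated 22 months gives about May 2021, so most Visit 8s have probably taken place. Section 9.7 already plans a safety cut after Visit 7. Both points stand. They shift the weight from procedure to reporting.

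4. **Same-day boosters need advance planning.** Visits 8 and 9 are to be combined where possible. This is a real inconvenience, but no Visit 8 assessment needs the list.

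A reader might infer that all AEs of the last six months were assessed by staff who knew the allocation. The documents do not support that: staff stay blinded until shortly before Visit 8, so only events first recorded or judged after the list arrives are affected. A reader might also infer that the 180 µg arm became open-label against the rest. That fails too, because 180 µg subjects excluded from the Day 208 per-protocol population stay mixed with the other two groups.

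**Conclusion.** The point holds for a defined part of the safety data. Unsolicited AEs and laboratory findings first recorded or judged at Visit 8 are assessed after site staff, and possibly the invited subjects, have learned who among the Day 208 per-protocol subjects received 180 µg. The affected look-back is about one third of the Main Study Phase, but only its non-severe, not previously reported events and the Visit 8 laboratory findings are exposed.

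The 83% figure rests on taking 81 as the length of the list. The subjects' own knowledge at the Visit 8 interview depends on when they are invited, which the protocol does not fix. The direction and size of any bias cannot be derived from the protocol. It is a specific route for bias into a tested secondary safety comparison, inexpensive to reduce, and it does not touch the primary conclusion.

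**What to change.** **For any Visit 8 still to come.** In section 4.2.10, disclose booster eligibility subject by subject, to investigator and subject alike, only after that subject's Visit 8 AE, causality and scripted safety entries, and the relevance of any laboratory results already available, are saved in the EDC. Apply the same rule on combined Visit 8/9 days, with the save opening Visit 9. Results that return later should be marked as judged after disclosure. If unblinded site staff are to hold the list until then, section 4.2.10 must also be amended where it bars them from any other part in trial conduct.

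**For Visit 8s already done.** In the Main Study analysis, place the between-group comparison of unsolicited and related unsolicited AEs recorded up to Visit 7 beside the Day 545 comparison. State that events first assessed at Visit 8 were judged after partial unblinding. The second interim analysis already cuts the safety data at Visit 7.

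**Cost.** A wording change, an EDC visibility rule and one extra AE table. Later disclosure makes same-day booster scheduling and consent less convenient.
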